6.2.1. Qualitative Visual Assessments

The images of each tracer recovered from the dual-tracer images as processed and output by the new dual-tracer processing algorithms will be visually assessed side-by-side with the original “true” single-tracer images. Tracer uptake throughout the body will be visually assessed for the presence of any artifacts, and regions of abnormal focal tracer uptake will be identified and compared for differences between the recovered and “true” images for each tracer. Any artifacts or differences in visual lesions will be marked and documented, and any such differences will be evaluated for any potential effect on the clinical interpretation of the images. All lesions identified will be marked, and quantitative analyses for each will be performed as described below.

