The PET/CT exams will be acquired at HCI, and the visual and semi-quantitative image assessments described in Section 5.0 will also be performed at HCI. The resulting images and assessment results will be de-identified and delivered to MFI, where the images will be analyzed and used for the Specific Aims of the research grant, including the analyses described in Section 6.0. Here, the separate-scan images obtained in each Arm will be combined to “synthesize” corresponding simultaneous dual-tracer images—enabling development and testing of various simultaneous dual-tracer processing algorithms, where the original single-tracer images provide “gold standard” references for recovering individual-tracer images from the combined dual-tracer ones. This is a well-established approach for developing rapid dual-tracer PET techniques [1-13], and in essence it allows for the data to act as their own controls.

This study is funded by National Cancer Institute grant 2R44CA257522, and it will be performed as part of a consortium agreement between MFI and the University of Utah under that grant. The overall goal is to develop techniques and algorithms for simultaneous dual-tracer imaging of these tracer pairs. This requires sets of dual-tracer PET data acquired using specially-designed multi-timepoint acquisition protocols that facilitate the development and study of simultaneous

dual-tracer PET imaging techniques. New algorithms for processing dual-tracer PET images will be developed and tested using these data. These algorithms are not part of any medical device, and the approach of using multi-timepoint dual-tracer PET scanning is novel and requires the development of new algorithms to process these data and recover individual-tracer PET images.

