4.4. Study Procedures, Schedule of Events, PET Tracer Administration: Route and Dosing

Patients enrolled in this study will receive all standard of care procedures as determined by their oncologist. The PET/CT exams performed at part of this study will be interpreted a nuclear medicine physician (sub-investigator [name]) and reported as a research note in the electronic health record. Identification of suspected lesions will be performed by the same physician and used for analysis as described below in the methods section.

The PET/CT exams may be performed in either order: FDG first or second, according to scheduling considerations and at the Investigator's discretion.

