5.1. Qualitative Visual Assessments

Visual assessment of the images for each tracer will be used to qualitatively assess for abnormal focal tracer uptake throughout the imaged body. Images will be reviewed in an unblinded manner to assess whether additional lesions are found when comparing with prior imaging. The coordinates of abnormal foci of uptake will be recorded and semi-quantitative assessments of these lesions will be computed as described below.

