5.2. Semi-Quantitative Assessments

Tracer uptake in each lesion identified in the qualitative visual analysis will be quantified by calculating body-weight-corrected Standardized Uptake Values (SUV_{bw}) as follows:

$$SUV_{max} = \frac{A_{max}}{\text{injected activity (mCi)} / \overline{BW}}$$

where $\overline{A_{max}}$ = radioactive concentration (mCi/mL)

\overline{BW} = body weight BW (g)

Corrections for lean body mass will also be performed to calculate the SUV_{lean} as follows:

$$\text{SUV}_{\text{lean}} = (\text{LBM}/\text{BW}) \times \text{SUV}_{\text{bw}}$$

where SUV_{bw} = the SUV measurements using body-weight corrections

LBM = the lean body mass estimated from the Janhasastian Formula [98]

A region-of-interest (ROI) will be drawn over the lesions (on all image slices with abnormal uptake). The mean value in each ROI will be computed to obtain the SUV_{mean} for each tracer, and the maximum value in each ROI will be computed to obtain the SUV_{max} for each tracer.

The location, ROI, SUV_{mean}, and SUV_{max} for each lesion will be recorded and used for data analysis.

6.0 **DATA ANALYSIS AND STATISTICS**

The de-identified images with marked lesion locations will be provided to MFI for further analysis according to the aims of grant 2R44CA257522. The imaging data will be used to develop dual-tracer PET scanning protocols and new processing algorithms for imaging FDG + Cu64-DOTATATE, FDG + Ga68-DOTATE, and FDG + Ga68-PSMA-11. Since a dual-tracer PET image is essentially the sum of two single-tracer PET images, this research will make use of the synthesized dual-tracer evaluation technique summarized below.

6.1. **Synthesized Dual-Tracer Evaluation Technique**

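### Recovered images are read for lesions only beside the true image, so a visual finding that lesion detection is unchanged may be too favourable

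*Combined protocol and SAP*

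**What the plan says.** Section 6.2.1 (Qualitative Visual Assessments) says that the recovered images "will be visually assessed side-by-side with the original" single-tracer images, and that "regions of abnormal focal tracer uptake will be identified and compared for differences between the recovered and" true images. Artifacts and lesion differences found in this way are documented and assessed for whether they could alter the clinical reading, and every lesion identified goes on to the quantitative analysis.

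Lesion locations are already on file by then. Section 5.1 has the single-tracer images read first: "The coordinates of abnormal foci of uptake will be recorded". Section 5.2 adds a region of interest and SUVs for each lesion. The opening of Section 6.0 then says: "The de-identified images with marked lesion locations will be provided to MFI for further analysis". Section 1.0 places the Section 5 assessments at the clinical site and the Section 6 analyses at the sponsor company, "where the images will be analyzed and used for the Specific Aims of the research grant, including the analyses described in Section 6.0".

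The only statement about blinding concerns the single-tracer read in Section 5.1: "Images will be reviewed in an unblinded manner to assess whether additional lesions are found when comparing with prior imaging". Nothing is said about masking, read order or a separate first look for the recovered images.

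**The concern.** If lesion detection on a recovered image is to be described as unchanged, the relevant question is what a reader would report from that image without its reference. In clinical use of simultaneous dual-tracer scanning there would be no separate single-tracer image to look at. Under Section 6.2.1 the reader always has it. A focus that is faint on the recovered image may be called present because the adjacent image shows where to look.

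Section 6.2.1 is the plan's only check on whether recovered images would change clinical interpretation, and the only place where missed or extra lesions would be noted as reading findings. The read also decides which additional foci, beyond those already marked on the single-tracer images, reach the region-of-interest analysis.

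**Working it through.** **Is there a figure to reproduce?** The plan states no target, agreement statistic or sample size for the visual read. Its one sample-size figure, N = 104 in Section 6.3, concerns SUVmean. It reproduces as 2 × (1.960 + 1.645)² × (10/5)² = 103.96, rounded up to 104, the per-group number for two independent groups. It plays no part in this point. The rest of the check is mainly a reading of the text.

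**What the reader has in view**

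1. Lesion coordinates and regions are recorded on the single-tracer images (Sections 5.1 and 5.2). Section 4.4 assigns this to one person: "Identification of suspected lesions will be performed by the same physician" who interprets the scans.
2. The marked images go to the sponsor company (opening of Section 6.0), where the Section 6 analyses are done (Section 1.0).
3. In Section 6.2.1, finding foci and comparing them happen in one side-by-side sitting.
4. No section adds a read of the recovered image alone, a masked read or a prescribed order.

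Item 3 is explicit and is enough for the point. Display of the marks during that sitting is inferred from items 1 and 2. Section 6.2.1 does not name the reader.

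**What depends on this read**

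- The four targets in Section 6.2.3 are correlation, slope, intercept and SUV difference. None uses the visual read.
- The pixelwise regression in Section 6.2.2 covers all pixels and does not depend on what a reader sees.
- The region-of-interest comparison uses lesions already marked. A lesion lost in recovery would show as a low recovered SUV at its known location.
- A focus present only on the recovered image has no prior mark. It enters the region-of-interest analysis only if this read records it.
- The statement on clinical interpretation rests on this read alone.

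**Would the pixelwise regression catch a small false focus?** Section 4.1.1 sets 1 cm as the minimum size of the qualifying lesion. A sphere of that diameter has volume π/6 × 1³ = 0.52 mL. Against an assumed imaged volume of 30 to 60 L, this is 0.52/30,000 = 0.0017% down to 0.52/60,000 = 0.0009% of the pixels. One such focus would barely move a whole-image slope or correlation.

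**Illustration of cueing (all inputs assumed)**

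Let s be the share of lesions a reader would detect on the recovered image alone, and c the share of otherwise missed lesions called present because the location is known. Apparent detection is s + (1 − s)c.

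| s | c = 0.25 | c = 0.50 | c = 0.75 |
|---|---|---|---|
| 0.80 | 0.85 | 0.90 | 0.95 |
| 0.90 | 0.925 | 0.95 | 0.975 |

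In counts, 2 lesions in each of 15 subjects is 30, and 3 in each of 20 is 60. With s = 0.90 there would be 30 × 0.10 = 3 to 60 × 0.10 = 6 true misses per arm. All would be hidden only if c = 1, so 3 to 6 is an upper bound for those inputs. The formula covers missed lesions only, not artifacts or extra foci.

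**The case against.** The strongest reply is that the visual read decides nothing. Equivalence is to be concluded from four numerical targets, and the marks that might cue a reader are what allow recovered and true SUVs to be compared lesion by lesion. This stands. A reader might infer that the equivalence conclusion itself is biased, or that lost lesions would vanish from the record. The documents support neither.

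Second, Section 6.2.1 describes a search for discrepancies, and having the reference alongside can make these easier to see. An extra focus with no counterpart on the adjacent image is exactly what the section asks to have documented. This also stands. It is tempting to say that the layout pushes every visual finding toward agreement; that goes too far. The direction is clear for faint lesions and uncertain for artifacts and extra foci.

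Third, it may be inferred that the algorithm's developers read the images with the marks on screen. Section 1.0 places the work at the company, but no section names the reader or says that the marks are displayed.

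Fourth, side-by-side viewing is a reasonable way to develop an algorithm, and the protocol describes its purpose as development. That is a reason to keep the step. It does not make a cued read adequate support for a statement that lesion detection or clinical interpretation is unaffected.

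**Conclusion.** The point holds in a limited form. The plan provides no read of recovered images without the true image in view, so a visual conclusion that lesions are equally well detected, or that clinical interpretation is unchanged, may be too favourable. The size cannot be obtained from the documents; the figures above only show how assumed cueing would act.

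The effect is confined to the visual lesion and clinical-interpretation conclusions and to which additional foci reach the region-of-interest analysis. The targets in Section 6.2.3 are not affected by this read. The conclusion rests on the explicit side-by-side wording and on the absence of any separate read; it does not require that the marks be displayed or that any particular person be the reader.

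**What to change.** In Section 6.2.1, for the final version of the algorithm, split the read into two steps carried out by whoever already performs it.

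1. Present each recovered image alone, in shuffled order, with the true image and the lesion marks hidden. Mark lesions and artifacts, and lock those marks.
2. Open the side-by-side view and classify every difference, as the section now intends.

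Report the counts of missed and extra lesions from the locked read. Name the reader's role and state whether that person had already read the true images: hiding them removes direct cueing, but recall would remain. Side-by-side viewing during development can continue unchanged.

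The cost is added reading time. No extra reader or scan is needed.

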6.2.2. Quantitative Performance Measures

Pixelwise Linear Regression Analysis: The overall accuracy of image pixels for each tracer will be measured by performing linear regression analysis for recovered vs. true image pixel values over all image pixels. This will be computed for each tracer for each patient. The regression slope, intercept, and Pearson’s correlation coefficient will be used as measures of bias between the recovered and true image pixels.

Linear Regression Analysis of ROIs: The accuracy of ROI values for lesions and normal background tissues will also be measured using linear regression analysis of the recovered vs. true values. The regression slope, intercept, and Pearson’s correlation coefficient will be used as measures of bias between the recovered and true ROI values.

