3.2.5. Human Radiation Dosimetry for CT Scans

CT scans are performed as part of PET/CT scans for both PET attenuation correction and anatomic localization. Each PET/CT exam performed in this study will include a CT scan. Since the subjects undergo 2 separate PET/CT exams, they will receive a total of 2 CT scans.

The study will be performed on research PET/CT scanners in the Molecular Imaging Suite at HCl. The previous scanner was a GE Discovery 710 PET/CT scanner and was used for dosimetry calculations. This scanner was replaced with a United Imaging uMI 780 PET/CT scanner and a uMI Panorama PET/CT. While this does not affect the dosimetry for the PET tracers, it may affect dosimetry for CT scans. The CT parameters for both new scanners have been adapted to achieve comparable dosimetry to those specified for the current GE D710 scanner. A helical CT scan will be acquired from the top of the head through the knees with moderate dose technique for both anatomical localization and attenuation correction. The original GE CT acquisition parameters for large patients receiving the greatest exposure were be 140 kVp, 0.5s rotation speed, 250 mA tube current, 64 x 1.25 mm collimation, and a pitch of 1.35 for the helical scan. Note that smaller patients will utilize 120 kVp but dosimetry estimates are based on larger patients at 140 kVp. Automatic tube current modulation is used for all CT exams but for the purpose of estimating maximum risk, a maximum fixed tube current of 250 mA is used for all calculations in order to provide a conservative estimate of maximum risk. In order to estimate the absorbed doses of individual organs and the resulting effective dose, the ImPACT Scan CT Patient Dosimetry Calculator (Version 1.0.4) was used with the specific acquisition parameters used in this protocol and the NRPB Monte Carlo dose data sets for the GE Lightspeed VCT scanner produced in report SR250 dosimetry tables.3-5 A correction factor has been applied to account for the difference in the CT Dose index (CTDI_{vol}) derived from ImPACT Calculator and that reported on the GE scanner. Note that the topogram contributes a negligible radiation exposure to the helical CT exam and was not included in the dose

estimates. The greatest organ absorbed doses for a single helical body CT scan using the aforementioned acquisition parameters are bone surfaces (28 mGy) and thyroid (27 mGy), while the effective dose is 17 mSv (Tables 1-3).

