4.2. Exclusion Criteria

[figure not shown]
- Patients with known intolerance or hypersensitivity to any somatostatin analogs will be excluded from the study Arms involving DOTATATE (Arms 1-2).
- Patients with known allergic or hypersensitivity reactions to previously administered radiopharmaceuticals
- Patients who require monitored anesthesia for PET/CT scanning.
- Patients who are too claustrophobic to undergo PET/CT scanning.
- Patients who exceed the 450 lb. weight limit of the PET/CT scanner.
- Patients who are pregnant or currently breast feeding.

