4.4.8. After Study Procedures

All images will be reconstructed and processed using the same parameters in order to ensure that there are no differences in processing. The PET/CT images will be transferred to the research DICOM database, and de-identified copies will be delivered to MultiFunctional Imaging LLC for processing and analysis according to the Specific Aims of the grant R44CA257522-02.

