6.2. Dual- vs. Single-Tracer Performance Assessments

The PET images for each tracer pair will be co-registered and combined to synthesize corresponding dual-tracer images. Dual-tracer processing algorithms, based on modeling differences in radioactive decay rates and kinetic distributions for each tracer, will be developed that take simultaneous dual-tracer PET images as input and out separate, recovered images of each individual tracer. The performance of the dual-tracer scanning approach and processing algorithms will be evaluated by comparing output images for each tracer to the corresponding original single-tracer images for that tracer. A number of analyses will be performed on these data.

In the following paragraphs, “recovered” is used to denote measures (image pixel values, SUVs) for individual-tracer images recovered from the dual-tracer images, and “true” is used to denote the corresponding value from the original constituent single-tracer image. This analysis evaluates how accurately the simultaneous dual-tracer imaging technique can recover individual images of each tracer, as compared to the images from conventional single-tracer scans.

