6.2.3. Quantitative Performance Targets

The following quantitative performance targets have been set in order to conclude that the new simultaneous dual-tracer techniques provide images of each tracer that are equivalent to images that would be obtained from separate, single-tracer scans of each tracer:

- (1) dual-vs.-single correlation coefficients ≥ 0.95 for both image voxels and lesion SUVs;

- (2) bias, as measured by the linear regression slope, to be within 5% of 1.0 ($0.95 \leq \text{slope} \leq 1.05$);
- (3) bias, as measured by the linear regression intercept, to be within 5% (of mean voxel or SUV value) of zero; and
- (4) tumor and background tissue SUVs for dual-tracer images within 0.05 of those for the separate-scan standard images (to 95% power).

These analyses will be repeated for all 3 tracer pairs.

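### The voxel regression runs over all image pixels with no body mask, so the voxel parts of targets (1) to (3) depend partly on air outside the patient

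*Combined protocol and SAP*

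**What the plan says.** Section 6.2.2 assesses voxel accuracy by "performing linear regression analysis for recovered vs. true image pixel values over all image pixels", and adds: "This will be computed for each tracer for each patient". Slope, intercept and Pearson's correlation are taken from that fit. A second regression uses ROI values for lesions and normal background tissue.

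Section 6.2.3 turns these into conditions for concluding equivalence with separate single-tracer images. Target (1) is "dual-vs.-single correlation coefficients ≥ 0.95 for both image voxels and lesion SUVs". Target (2) requires a slope between 0.95 and 1.05. Target (3) requires an intercept within 5% of the mean voxel or SUV value. Target (4) limits the difference in tumour and background SUV to 0.05.

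No section defines a body mask, an uptake threshold or any exclusion of voxels outside the patient. On image preparation, Section 6.2 says "The PET images for each tracer pair will be co-registered and combined to synthesize corresponding dual-tracer images", without naming the reference exam. Section 3.2.5 says of the subjects that "they will receive a total of 2 CT scans", one with each exam.

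**The concern.** A whole-body PET image is a rectangular block that includes air around the patient. If air is near zero in both the recovered and the true image, those voxels form a cluster at the origin. The cluster widens the spread of true values and adds little error, so the correlation rises. It also pulls the fitted line towards the origin and towards the point of mean uptake, which can bring a wrong slope and intercept closer to 1 and 0.

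The targets are meant to describe recovery of tracer uptake in the patient. If the voxel fit includes air, the same in-body recovery can meet or miss a target according to how much air is in the image and how noisy it is. The voxel part of target (1) is also the only numerical target that addresses voxel-level scatter over the whole image. Slope and intercept do not measure scatter, and ROI means average much of it away.

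**Working it through.** **The plan's own figure.** The plan gives no calculation behind the voxel targets. Its only computed figure is N = 104 in Section 6.3. A two-group normal formula reproduces it: 2 × (1.960 + 1.645)² × (0.10/0.05)² = 103.97, rounded up to 104. Nothing below depends on it.

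**Inputs.** From the documents: the voxel set (all pixels), correlation limit 0.95, slope limits 0.95–1.05, intercept limit 5% of the mean. Assumed, because the documents give none:
- body share of voxels f = 0.2–0.5 (0.2–0.7 for the slope check), with k = 1 − f;
- in-body coefficient of variation CV = 0.5, 1.0 or 2.0, with v = CV²;
- air error SD equal to a times the in-body error SD, with a = 0, 0.3 or 0.5;
- body mean scaled to 1 and true air value 0.

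**Correlation.** Take in-body slope 1, intercept 0 and error variance s². Then
- in-body: r² = v / (v + s²)
- all pixels: r² = (v + k) / (v + k + s²(1 + k a²/f))

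Since 1/0.95² − 1 = 0.10803, the largest s² that passes is 0.10803 v inside the body and 0.10803 (v + k)/(1 + k a²/f) over all pixels.

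Example with f = 0.2, CV = 0.5, a = 0: s² = 0.10803 × 1.05 = 0.1134. In-body r = √(0.25/0.3634) = 0.829. The allowed RMS error is √(1.05/0.25) = 2.05 times the body-only limit.

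Over f = 0.2–0.5:

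| CV | In-body r at all-pixel r 0.95, a = 0 | a = 0.3 | a = 0.5 | Allowed RMS error vs body-only, a = 0 | a = 0.5 |
|---|---|---|---|---|---|
| 0.5 | 0.829–0.869 | 0.864–0.878 | 0.888–0.903 | 1.73–2.05 | 1.45–1.57 |
| 1.0 | 0.915–0.928 | 0.931–0.935 | 0.941–0.955 | 1.22–1.34 | 0.95–1.10 |
| 2.0 | 0.941–0.944 | 0.949–0.955 | 0.955–0.969 | 1.06–1.10 | 0.77–0.95 |

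The two limits are equal when a = √f/CV. That is 0.89–1.41 at CV 0.5, 0.45–0.71 at CV 1.0 and 0.22–0.35 at CV 2.0. Above that value, including air makes the target stricter.

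**Slope and intercept.** Take an in-body loss of contrast, y = 0.9x + 0.1, with zero air. Inside the body the slope of 0.90 fails target (2), and the intercept of 10% of the mean fails target (3). Over all pixels, slope = (0.9v + k)/(v + k). Both image means equal f, so the intercept divided by the mean is 1 − slope.
- CV 0.5: f = 0.2 gives 1.025/1.05 = 0.976 and intercept 2.4%. f = 0.7 gives 0.525/0.55 = 0.955 and 4.5%. Both targets pass.
- CV 1.0: f = 0.2 gives 1.7/1.8 = 0.944 and 5.6%. f = 0.7 gives 1.2/1.3 = 0.923 and 7.7%. Both targets still fail.

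For a purely proportional error, y = bx with zero air, the slope is b in either fit, so it stays visible.

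**Effect of a mask on target (3).** If an offset c covers the whole image including air, both fits give intercept c. The limit is 5% of f over all pixels and 5% of 1 inside the body. Masking therefore makes this limit 1/f times looser, or 2 to 5 times at f = 0.5–0.2.

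**The case against.** The plan names its voxel set openly and applies the limits to image voxels. Nothing says that 0.95 was meant for a body-only fit, so looser is a comparison with a benchmark the plan did not choose. That is fair. But the targets serve a conclusion about patient images, and their result should not turn on air.

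Direction and size are not established. The table runs from 2.05 times looser to 0.77 times, which is stricter. The large figures need low in-body variability, and the dosimetry hints at uneven uptake. In Table 3 the absorbed dose ratio is 96.19/2.67 = 36 for kidney to muscle with PSMA and 72.15/5.55 = 13 for bladder to muscle with FDG. Absorbed dose is only a rough proxy for voxel SUV, but this favours the smaller effects. The objection stands as a limit on size, not on the dependence itself.

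Other checks remain. If the contrast loss above holds in the ROIs too, an ROI mean follows the same line, so the ROI slope is 0.90 and fails. Section 6.2.1 adds visual review for artefacts.

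A reader might also infer that heavier patients face a different pass mark, because the fit is per patient, weights up to 450 lb are allowed and Section 4.4.8 says "All images will be reconstructed and processed using the same parameters". The documents do not support that. They do not state one in-plane field of view, and Section 4.4.4 has the field of view selected after the topogram. The contrast is also fragile. At CV 1.0 and in-body r 0.92, all-pixel r is 0.953 at f = 0.2 and 0.944 at f = 0.5 with clean air, but 0.938 and 0.940 at a = 0.3, which fails at both.

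**Conclusion.** The point holds in limited form and is minor. With no body mask, the voxel parts of targets (1) to (3) depend partly on voxels outside the patient. With clean air and f = 0.2–0.5, an all-pixel correlation of 0.95 accepts an in-body correlation as low as 0.829 at CV 0.5, but only 0.941 at CV 2.0. An in-body contrast loss can also pass the slope and intercept targets at CV 0.5, though not at CV 1.0. These sizes rest on assumed body share, variability and air error.

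Three stronger readings are not supported. The targets are not always looser, because air error above √f/CV times the in-body error reverses the effect on the correlation. False overall equivalence is not shown, because the lesion and ROI parts and target (4) contain no air. A mask would not turn r ≥ 0.95 into a fixed error limit: body-only, it still allows an RMS error of √0.10803 × CV, which is 16%, 33% or 66% of the body mean at CV 0.5, 1.0 or 2.0.

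**What to change.** In Section 6.2.2, run the voxel regression over voxels inside a body contour taken from the CT of the exam that serves as co-registration reference. Name that exam in advance, because each subject has two CTs. The first exam is a natural choice, since Section 4.4.4 already repositions the patient to match it. In Section 6.2.3, apply voxel targets (1) to (3) to those voxels.

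Keep the all-pixel fit and report it alongside, with its intercept set against 5% of the all-pixel mean. This keeps errors outside the body in view and covers the case where masking loosens target (3) by 1/f.

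The cost is a masking step and a check of the contour after co-registration. No new acquisition is needed: every exam includes a CT, and its range from head to knees (Section 3.2.5) covers the eyes-to-thighs PET range (Section 4.4.4). The voxel figures may look less favourable than over all pixels.
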